**Noninvasive Ventilation for Preterm Neonates With
Respiratory Distress Syndrome: a Multi-center Randomized
Controlled Trial**

(NCT03099694)

13 July 2017

Solid PDF/A Express
<http://www.SolidDocuments.com/>

STUDY PROTOCOL

Noninvasive high-frequency oscillatory ventilation versus nasal continuous positive airway pressure in preterm infants with respiratory distress syndrome: Study protocol for a multi-center, prospective, randomized, controlled trial. For the Noninvasive High-Frequency Oscillatory Ventilation Study Group (NHFOV Study Group*).

Abstract

Background: Invasive mechanical ventilation is associated with development of adverse pulmonary and non-pulmonary outcomes in very low birth weight infants. Various modes of non-invasive respiratory support are being increasingly used to decrease the incidence of bronchopulmonary dysplasia (BPD). The aim of this trial is to compare the effect of noninvasive high-frequency oscillatory ventilation (NHFOV) and nasal continuous positive airway pressure (NCPAP) in preterm infants with respiratory distress syndrome (RDS) as a primary noninvasive ventilation support mode.

Methods/Design: In this multicenter, randomized, controlled trial, 300 preterm infants born at gestational age (GA) less than 34 weeks with a diagnosis of RDS will be randomized to NHFOV or NCPAP as a primary mode of noninvasive respiratory support. Study will be conducted in 18 tertiary neonatal intensive care units in China. The primary outcome is the need for invasive mechanical ventilation (IMV) during the first 7 days after enrollment in preterm infants randomized to the two groups. The

prespecified secondary outcomes include days of hospitalization, days on noninvasive respiratory support, days on IMV, days on supplemental oxygen, mortality, need for surfactant, severe retinopathy of prematurity(ROP) requiring laser or surgery, patent ductus arteriosus needing ligation, bronchopulmonary dysplasia(BPD), occurrence of abdominal distention, air leaksyndromes, intraventricular hemorrhage (IVH \geq grade 3), necrotizing enterocolitis (NEC \geq II stage) and nasal trauma. Other secondary outcomes include Bayley Scales of Infant Development at 18-24 months of corrected age.

Trial registration: ClinicalTrials.gov Identifier: NCT03099694.

Key words: Noninvasive high-frequency oscillatory ventilation; nasal continuous positive airway pressure; respiratory distress syndrome; preterm infants; surfactant; invasive mechanical ventilation

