Background

Respiratory distress syndrome (RDS) due to surfactant deficiency is the leading cause of respiratory failure in preterm infants [1]. Early noninvasive positive pressure ventilation has become a recommended strategy for respiratory management of preterm infants with RDS [2]. In addition to nasal continuous positive airway pressure (NCPAP), various types of noninvasive ventilation (NIV) modes have been used in the treatment of RDS including heated, humidified, high-flow nasal cannula (HHFNC), biphasic NCPAP (BP-NCPAP) and nasal intermittent positive airway pressure (NIPPV) [3]. However, clinical trials have shown that 25 to 67% of very low birth weight preterm infants fail these NIV modes and require IMV [4-5]. To minimize the need of IMV, noninvasive high-frequency oscillatory ventilation (NHFOV) has been studied as a rescue treatment after failure of other NIV modes or following extubation from IMV during weaning phase [6]. However, to date, no studies have been published on the efficacy of NHFOV as a primary mode of respiratory support in preterm infants. In the present trial, we aim to compare the effect of NHFOV and NCPAP in preterm infants with RDS as a primary NIV mode. Our main hypothesis is that NHFOV is more effective in the treatment of preterm infants with RDS than NCPAP when used as a primary NIV mode.

Trial Design

Aim

The primary aim of this trial is to compare the need for IMV during the first 7 days of life in infants randomized to NHFOV versus NCPAP.

Study design

This will be a multi-center, prospective, randomized controlled trial conducted in 18 tertiary neonatal intensive care units (NICUs) in China. The trial will be performed in accordance with prospective trial flow (Fig.1).

Inclusion criteria:

(1) Gestational age (GA) is from 26 weeks 0 days (26⁺⁰weeks) to 33 weeks 6 days(33⁺⁰weeks) (estimated on the postmenstrual date and early gestation ultrasonographic findings); (2) diagnosis of RDS. The diagnosis of RDS will be based on clinical manifestations(tachypnea, nasal flaring and or grunting) and the typical X-ray picture of RDS (grain shadow, air bronchogram or white lung)-see appendix; (3) RDS Silverman score>5; (4) Age <12 hours; (5) informed parental consent has been obtained.

Exclusion criteria

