since these are supposed to be the best in terms of resistive charge, leaks and/of comfort. Nasal prongs size will be chosen according to the nares' diameter as the best fitting ones (the largest ones that fit the nares without blanching the surrounding tissues) and following manufacturer's recommendations. Particular care (e.g.: pacifiers, positioning, nursing) will be applied to reduce leaks and improve patients' comfort. These matters will be evaluated through a dedicated 30 min observation period when study intervention will be instigated.

Ventilatory management

The two different respiratory supports will be managed as follows:

CPAP: Neonates assigned to the CPAP group were initiated on a pressure of 5 cmH₂O. CPAP can be raised in steps of 1 cmH₂O up to 10 cmH₂O. If this is not enough to maintain target oxygen saturation (SpO₂) from 89% to 92% in preterm infants <30 weeks GA and 90-94% in infants ≥30 weeks GA by pulse oximeter, FiO₂ will be added up to 0.40.

NHFOV: For Medin CNO, the initial NHFOV settings will be: mean airway pressure (MAP) of 6cmH₂O (range 6-10cmH₂O), frequency of 10 Hz (range 6-12), The Medin CNO has ten grades of amplitude. grade 7th amplitude will be to start with (grade range 7th-10th). For SLE 5000, The initial settings will be: MAP of 6 cm H₂O (range 6-10cmH₂O); frequency of 10Hz (range 6-12), inspiratory time 50% (1:1), oscillations of amplitude of 20 cm H₂O (range 20-35 cm H₂O). It is not strictly necessary to have visible chest oscillations, as most of the CO₂ elimination during NHFOV will occur in the upper airway dead space. Maximal allowed FiO₂ will be 0.40 and SpO₂ from 89% to 93% in

preterm infants <30 weeks GA and 90-94% in infants \geq 30 weeks GA by pulse oximeter.

Surfactant Therapy

Surfactant (Poractant alfa, Chiesi Pharmaceuticals, Parma, Italy) at dose of 200 mg/kg will be administered via INSURE method if infant presents with the following: infants \leq 26 week's gestation when FiO_2 requirement >0.30 and infants >26 week's gestation when FiO_2 requirement >0.40 [2]. Additional doses of surfactant may be given using INSURE technique at the discretion of the clinician.

Caffeine Therapy

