Caffeine (Caffeine Citrate Injection, Chiesi Pharmaceuticals, Parma, Italy) will be administered when infants present with moderate apnea (defined as 3 or more episodes in 24 hours or a single episode requiring resuscitation and bag-mask ventilation). The initial loading dose is 20mg/kg, and the maintenance dose is 5mg/kg per day.

Weaning from study interventions

The criteria for weaning noninvasive respiratory will be: (1) minimal or no signs of respiratory distress (RDS Silverman score < 5) ; (2) NHFOV MAP or NCPAP pressure <6 cmH₂O and (3) $FiO_2 < 0.25$ to achieve target SpO₂.

Criteria for intubation and IMV

These will be as follows [10-11]: (1)severe respiratory acidosis ($P_aCO_2 > 65$ mmHg with $pH < 7.20$);(2)severe apnea and bradycardia (defined as recurrent apnea with >3 episodes per hour associated with heart rate < 100 /min, a single episode of apnea that

requires bag and mask ventilation); (3) hypoxia ($FiO_2 > 0.5$ with $PaO_2 < 50$ mmHg), severe respiratory distress (RDS Silverman score > 7); (4) pulmonary hemorrhage; (5) pneumothorax; (6) cardiopulmonary arrest needing chest compressions.

Training

Since not all clinicians are well versed in all respiratory techniques and, particularly, NHFOV is a relatively new technique, the training is capital for the trial success. The protocol will be diffused between participating centers at least 3 months before the study begins. One investigator (YS) will explain the study protocol in an in-person meeting with all investigators. During the two months' period, clinicians will familiarize with the protocol and the respiratory techniques and the two co-principal investigators will be available to solve any doubt. A dedicated social media chat has been set to facilitate these exchanges. The trial is supposed to actually start in July 2017.

Outcomes

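### Weaning requires an NHFOV mean airway pressure below 6 cmH₂O, but the protocol lists only 6 to 10 and describes no step-down below that

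*Combined protocol and SAP*

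**What the plan says.** The section Weaning from study interventions sets three criteria that must all hold: a Silverman score below 5 with little or no distress, a pressure criterion, and FiO₂ below 0.25 at target saturation. The pressure criterion is "NHFOV MAP or NCPAP pressure <6 cmH₂O". It names NHFOV MAP, so it is not a rule for NCPAP alone.

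The section Ventilatory management gives the pressures:

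- NHFOV on the Medin device: "the initial NHFOV settings will be: mean airway pressure (MAP) of 6cmH₂O (range 6-10cmH₂O".
- NHFOV on the other device: "For SLE 5000, The initial settings will be: MAP of 6 cm H₂O (range 6-10cmH₂O".
- NCPAP: "Neonates assigned to the CPAP group were initiated on a pressure of 5 cmH₂O", and then "CPAP can be raised in steps of 1 cmH₂O up to 10 cmH₂O".

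No other NHFOV MAP range appears in the protocol, and no sentence expressly permits MAP below 6. No lower limit is stated for NCPAP.

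Time on noninvasive support is a secondary outcome. The Abstract lists "days of hospitalization, days on noninvasive respiratory support, days on IMV" among the secondary outcomes, and the Outcomes section includes days on noninvasive ventilation.

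**The concern.** The weaning threshold is strict and shared by the arms, but the listed pressures are not. The NCPAP arm has a listed pressure below 6, which is its starting value. The NHFOV arm has none. A clinician with an NHFOV infant who meets the Silverman and FiO₂ criteria at a MAP of 6 must do one of three things: go below the only range in the protocol, keep the infant on NHFOV, or wean against the criterion. Stepping down to NCPAP is not an obvious way out, because the Randomization section rules out crossover between arms.

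The weaning rule helps to determine how long support lasts. If some of the 18 sites keep to the range and others do not, days on noninvasive ventilation will partly measure how each site read the text, and only in the NHFOV arm. Statistical methods plans a t-test for continuous data and describes no adjustment for site. Randomization is stratified by gestational age only.

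**Working it through.** The protocol states no figure on this point to reproduce. The check compares the listed pressures with the threshold.

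**Inputs.** NHFOV MAP: start 6, range 6 to 10, both devices (Ventilatory management). NCPAP: start 5, steps of 1, ceiling 10 (same section). Threshold: strictly below 6 (Weaning from study interventions). No step size is given for NHFOV MAP. Steps of 1 are used here for counting, but the result does not depend on them, since every value from 6 to 10 is at least 6.

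| Arm | Listed pressures (cmH₂O) | Values below 6 |
|---|---|---|
| NHFOV, either device | 6, 7, 8, 9, 10 | none (0 of 5) |
| NCPAP, start to ceiling | 5, 6, 7, 8, 9, 10 | 5 (1 of 6) |

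**When it matters.** Entry requires "RDS Silverman score>5" and weaning requires a score below 5, so no infant in either arm qualifies for weaning at entry. The question arises later, once the Silverman and FiO₂ criteria are met.

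**Two infants at starting settings.** Suppose both now have a Silverman score below 5 and FiO₂ below 0.25. The NCPAP infant, at 5, meets all three criteria. The NHFOV infant, at 6, fails the pressure criterion. An NCPAP infant who had been raised to 6 or more would also have to come down, but to a pressure that the protocol names.

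**The possible readings of 6 to 10.**

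1. Operating range: no listed NHFOV pressure meets the rule.
2. Range for initial settings only: MAP may later go below 6, but the protocol does not say so, or how far.
3. Escalation range, with 6 as the start, 10 as the ceiling, and MAP lowered below 6 to wean: the rule can be met, but the step-down is again not described.

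**After the fix.** With MAP allowed down to 5 for weaning, the NHFOV arm has one qualifying value, 5, the same as NCPAP.

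**The case against.** A reader might infer that the two sections flatly contradict each other and that NHFOV infants cannot be weaned at all. The documents do not support that. For both devices the MAP range stands in a sentence about initial settings. The weaning criterion itself names NHFOV MAP below 6, which presupposes that MAP can be lowered there. The escalation reading also fits the layout: MAP starts at the bottom of its range, as does amplitude on the Medin device, "grade 7th amplitude will be to start with (grade range 7th-10th", and amplitude on the SLE 5000 (20, range 20 to 35). Frequency does not follow this pattern (10 Hz, range 6 to 12). NCPAP is likewise described only as being raised from its start. This reading keeps a MAP ceiling of 10, so the absence of any other ceiling is no argument against it.

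Some features point the other way. The paragraph is introduced as describing how the two supports will be managed, and a single starting value needs no range unless the range governs later settings. The Discussion also criticises earlier trials for using widely varying NHFOV parameters, which fits an intent to bound them here. None of this settles the matter.

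The Training section provides an in-person meeting, a familiarisation period, access to the co-principal investigators and a chat. These are a real route for resolving the question. They do not change the text, and nothing shows that this question would be raised or answered alike at all sites.

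What stands of the objection is that this is an ambiguity, and that the investigators may well have intended a step-down below 6. What does not fall is that the step-down is unwritten under every reading, and that the gap lies in one arm only.

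**Conclusion.** The point holds as a clarification that should be made, with moderate confidence. Read literally as an operating range, none of the listed NHFOV pressures satisfies the weaning rule, and this would apply to all 150 infants planned for that arm. Read as an initial or escalation range, NHFOV infants still need a reduction below the listed values that the protocol does not describe.

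The consequence is confined to days on noninvasive ventilation. Sites that keep to the range would prolong NHFOV support, so part of an arm difference could come from the rule and not from recovery. The size is unknown. It depends on how many sites keep to the range and for how long infants are held, and the documents give neither. It is zero if sites lower MAP below 6.

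Two stronger inferences are not supported. A reader might want to state a bias in days, but any such figure would rest on an assumed delay. The pilot's 24.3% rate of invasive ventilation does not help, since it does not measure who reaches weaning. A reader might also infer an effect on the primary outcome. The intubation criteria do not refer to MAP or NCPAP pressure, and no such effect is claimed here.

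**What to change.** Add one sentence under Ventilatory management, for both NHFOV devices: *MAP may be reduced below 6 cmH₂O (to 5 cmH₂O) for weaning.* Repeat it in the training material so that all sites apply it alike.

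Leave the threshold below 6 and both starting pressures unchanged. The threshold causes no difficulty in the NCPAP arm, so there is no reason to alter it there.

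The cost is one sentence, with no change to sample size, randomisation or analysis. The downside is that NHFOV is used briefly below its listed range. An NHFOV infant at the starting pressure will still need one step down that an NCPAP infant at its starting pressure does not, but the step will be written and the same at every site.

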(1) Resuscitation requiring early intubation according to the American Academy of Pediatrics guidelines for neonatal resuscitation [8]; (2)major congenital malformations or known complex congenital heart disease; (3)pulmonary hemorrhage or pneumothorax; (4) congenital lung diseases or malformations or pulmonary hypoplasia;

Setting

We plan to enroll preterm infants born between 26 and 34 weeks of gestational age from 18 tertiary NICUs in China. These 18 tertiary NICUs have more than 800 NICU beds and annual admissions of nearly 8,000 preterm infants with RDS each year. The first (XZ) and last authors (RR) take responsibility for the accuracy and completeness

of the trial.

Randomization

To avoid the chance of having more infants in one group than another, block randomization will be applied, with a block size of 4. The envelopes are sealed, shuffled, and then numbered in sequential order from 1 to 4. A clinician who is not in the trial group will open the envelope and randomize patients. This procedure will be repeated for each group of four infants. Infants will be stratified according to 26^{0/7}-27^{6/7} weeks, 28^{0/7}-29^{6/7} weeks, 30^{0/7}-31^{6/7} weeks and 32^{0/7}-33^{6/7} weeks. Infants born from multiple gestations will be assigned by individual randomization. Infants randomized to one arm cannot crossover to the other or vice-versa during the study.

Trial intervention

Ventilators

CPAP: CPAP will be provided by continuous flow devices (CNO Medin, Germany or Carefusion, USA) Bubble CPAP devices will not be used.

NHFOV: NHFOV will be provided by two ventilators (CNO, Medin, Germany or SLE 5000, UK). The Medin CNC ventilator produces high-frequency oscillations by flow interruption with cyclic opening-closure of the end expiratory valve. Otherwise, The SLE 5000 ventilator is a time-cycled, pressure-limited and continuous-flow neonatal ventilator.

Before the beginning of the study all ventilators will be checked to ensure that there is no malfunction.

Interfaces

CPAP and NHFOV will be all administered through short, low-resistance binasal prongs,

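### Read literally, the hypoxia criterion for invasive ventilation (FiO2 above 0.5) cannot be met while the 0.40 FiO2 limit on the assigned support is followed

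*Combined protocol and SAP*

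**What the plan says.** All references are to the combined protocol and SAP.

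- **Ventilatory management, NHFOV:** "Maximal allowed FiO₂ will be 0.40".
- **Ventilatory management, CPAP:** pressure is raised in steps up to 10 cmH2O. If that does not hold the saturation target, "FiO₂ will be added up to 0.40". No step beyond that is given.
- **Surfactant Therapy:** surfactant by INSURE is triggered at an FiO2 requirement above 0.30 up to and including 26 weeks, and for "infants >26 week's gestation when FiO_2 requirement >0.40". After that, "Additional doses of surfactant may be given using INSURE technique at the discretion of the clinician".
- **Criteria for intubation and IMV:** item (3) lists "hypoxia ($FiO_2 > 0.5$ with $PaO_2 < 50$ mmHg" and, in the same item, "severe respiratory distress (RDS Silverman score > 7". The other items are severe respiratory acidosis, severe apnea with bradycardia, pulmonary hemorrhage, pneumothorax and cardiopulmonary arrest.
- **Randomization:** "Infants randomized to one arm cannot crossover to the other".
- **Outcomes:** the primary outcome is need for IMV in the first 7 days. Whether need means that IMV was given or that the criteria were met is not stated.

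**The concern.** The criterion that deals directly with failing oxygenation starts at an FiO2 that the protocol does not allow on either assigned support. An infant who reaches the limit and stays hypoxic has no written oxygenation route to IMV, and a switch to the other study mode is barred.

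This matters more than an ordinary drafting slip because the criteria govern the decision that produces the primary outcome. Eighteen units will apply them and no masking is described. If units resolve the conflict differently, similar infants may be counted differently, and a clinician who knows the allocation has room to decide either way.

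**Working it through.** No sample-size or error-rate figure is involved. The check sets the stated thresholds side by side.

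**1. Limit against criterion.**

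| Rule | FiO2 stated | Section |
|---|---|---|
| NHFOV limit | at most 0.40 | Ventilatory management |
| CPAP limit | up to 0.40 | Ventilatory management |
| Surfactant trigger, over 26 weeks | requirement above 0.40 | Surfactant Therapy |
| Hypoxia criterion for IMV | above 0.5, with PaO2 below 50 mmHg | Criteria for intubation and IMV |

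{FiO2 ≤ 0.40} ∩ {FiO2 > 0.5} = ∅. The distance is 0.50 − 0.40 = 0.10 in FiO2, and the stated numbers are the same in both arms. The PaO2 condition does not help, because it applies together with the FiO2 condition.

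**2. Is there bridging text?** None was found. No section lifts the limit, describes a step between 0.40 and 0.5, or says how an infant still hypoxic at 0.40 is to be handled.

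**3. The surfactant rule.** If requirement means delivered FiO2, the trigger above 26 weeks also lies outside the limit. If it means an estimated need, needs above 0.40 were foreseen, but the text does not say how need is judged at the limit. Neither reading raises the limit. The trigger of 0.30 for infants up to 26 weeks lies inside the limit and is unaffected.

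**4. Who is left without a written route?** Acidosis, apnea with bradycardia, Silverman score above 7, pulmonary hemorrhage, pneumothorax and arrest do not depend on FiO2. Before that point the protocol also allows pressure or mean airway pressure up to 10 cmH2O, and surfactant with discretionary repeats. What remains is the infant still hypoxic at the limit after those measures who meets none of the other criteria.

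**5. What happens to that infant in the data?** A site has at least three courses open. How each counts depends on what need for IMV means.

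| Site's course | Outcome = IMV received | Outcome = criteria met |
|---|---|---|
| Exceeds the limit, hypoxia criterion then met, IMV given | event | event |
| Gives IMV at or below 0.40, outside the criteria | event | no event |
| Continues at the limit, no other criterion met later | no event | no event |

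The same infant can be an event or a non-event. For scale, one infant changes the rate in an arm of 150 by 1/150 = 0.67 percentage points. The documents give nothing from which to derive how many infants this is, or whether they would fall unequally between the arms.

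**The case against.** The case on the other side has four parts.

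- **Other criteria will catch most of these infants.** Largely true, and it is why the affected group is narrow. A reader might infer that the primary outcome cannot be reached, or that part of it is lost. The documents do not support that, since every other criterion works without reference to FiO2.
- **Sites are not forced into a breach.** Also true. It is tempting to say that a site must either exceed the limit or intubate outside the criteria. But pressure or mean airway pressure can be adjusted within range, surfactant can be repeated, and the infant can be kept at the limit. The conflict permits divergent courses; it does not compel one.
- **The CPAP figure may be only a titration step.** The CPAP wording is less explicit than the NHFOV wording, which states a maximum. It gives the same number and no further step, so the plain reading is a common ceiling. If the looser reading were adopted, the two arms would be under different rules, which is another reason to settle the text.
- **Training will produce one reading.** The Training section provides an in-person meeting, and "the two co-principal investigators will be available to solve any doubt". This lowers the chance of divergence, but the documents record no agreed reading and the text stays as it is.

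A reader might also take the reference to intubation in the subgroup paragraph of Statistical methods as showing that the outcome is receipt of IMV, so that all these intubations count. That support is weak: INSURE, as Appendix A3 spells it out, itself begins with intubation, so the word alone does not identify IMV.

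**Conclusion.** The textual conflict is certain: within the stated limit, the hypoxia criterion cannot be met on the assigned support. Its reach is narrow, and its effect on the trial is unknown. The possible consequence is inconsistent decisions on a primary outcome event across 18 sites with no masking described.

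A reader might go further and infer bias between the arms or an unreliable result. The documents do not support this. The stated numbers are the same in both arms, the count of affected infants cannot be derived, and nothing shows that the conclusion would change.

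The verdict rests on three readings: 0.40 is a ceiling in the CPAP arm as well as the NHFOV arm; hypoxia and the Silverman score in item (3) are alternatives; and FiO2 in the criterion means the FiO2 delivered. Confidence is high on the conflict and low on any effect on the result.

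**What to change.** The investigators should reconcile three statements so that they are mutually consistent and read the same in both arms: the FiO2 limit in Ventilatory management, the threshold in Surfactant Therapy, and the hypoxia item in Criteria for intubation and IMV. The values are theirs to set. The CPAP and NHFOV limits should be worded alike, and the text should say whether an FiO2 requirement means delivered oxygen or estimated need.

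The Outcomes section should state whether the primary outcome is receipt of IMV or meeting the criteria, and should distinguish intubation for INSURE from IMV.

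The cost is a short protocol amendment, which can be passed to sites through the training channels already planned. It needs no extra patients.

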The primary outcome of this trial will be to determine the need for IMV in the first 7 days of life in preterm infants randomized to the two groups. Secondary outcomes include days of hospitalization, days on noninvasive ventilation, days on supplemental oxygen, pre-discharge mortality, surfactant doses, incidence of stage III ROP and BPD, occurrences of abdominal distention, air leaks, IVH \geq grade 3 and NEC. Secondary outcomes also include Bayley Scales of Infant Development at 18-24 months of corrected age. BPD will be defined according to the National Institutes of Health consensus definition as mild, moderate and severe BPD [12], IVH classification according to Papile et al [13] and for NEC, Bell staging will be used [14].

Data collection

Patient demographic data include: sex, birth weight, gestational age, Apgar scores, mode of

delivery, prenatal corticosteroid use, premature rupture of the membrane, RDS Silverman score and critical risk index for babies-II (CRIB-II) score. More details see in the appendix Clinical data :Including the need for IMV, days of hospitalization, days on noninvasive respiratory support, days on supplemental oxygen, mortality, the need for surfactant, occurrences of abdominal distention, air leaks, IVH \geq grade and NEC \geq stage II. More details see in the appendix Follow-up data: The incidence of BPD and ROP at a post-menstrual age of 36 weeks or at discharge, and Bayley Scales of Infant Development at 18-24 months of corrected age.

Sample size calculation

It is difficult to calculate a sample size for such a study, since it is the first to investigate NHFOV vs CPAP in primary support phase in preterm infants with RDS. There is only one preliminary study available about the primary outcome “need for IMV”. This pilot study conducted by Zhu et al provides data about the primary outcome “need for IMV”. This trial showed the need for IMV was significantly lower in the NHFOV compared with the NCPAP group (24.3% vs. 56.4%, $P < 0.01$). Considering an α -error of 0.05 and a power of 90%, 150 neonates should be enrolled in each arm (with a 1:1 design) to detect the same difference.

Statistical methods

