Data will be analyzed using SPSS version 19 software. The statistical analyses include Student's t-test for continuous data and compared proportions using Chi-squared test, and Fisher's exact test for categorical data. Predefined four subgroups are 26^{0/7}-27^{6/7} weeks, 28^{0/7}-29^{6/7} weeks, 30^{0/7}-31^{6/7} weeks and 32^{0/7}-33^{6/7} weeks, and subgroup analyses will be conducted for the primary outcome in the preterm infants. To further evaluate the effect of NHFOV on intubation within

subgroup, the test of treatment-by-gestational age subgroup interaction will also be done using the paired binary logistic regression. For the preterm infants lost to follow-up, the missing values of the primary and secondary outcomes are replaced using multiple imputation. A P -value < 0.05 will be regarded as statistically significant.

Data Safety Monitoring Board (DSMB): [name], Professor of Pediatrics, Oklahoma University Medical Center, Oklahoma, [name], Professor of Pediatrics, Medical College of Georgia, Georgia Health Sciences University, Augusta, Georgia, and [name], MD., MPH (Biostatistics and Epidemiology) Assistant Professor of Pediatrics, Keck School of Medicine of the University of Southern California, Los Angeles, California will serve as DSMB members. [name] will also serve as consultant for statistical analysis.

Registration number

The trial has been approved by the centralized ethics committee (The Ethics Committee of Daping Hospital, Research Institute of Surgery, Third Military Medical University) and registered at <http://www.clinicaltrials.gov>(ID: NCT03099694).

Discussion

In the past decades, several clinical trials have compared the effects between NHFOV and NCPAP in neonates as a rescue mode or during weaning from IMV. These trials demonstrated that NHFOV applied with nasopharyngeal tube are more beneficial than NCPAP in reducing CO₂ levels [16-19]. Recently, two retrospective case series also reported NHFOV could be applied in preterm infants as a rescue treatment after the

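### Day-count outcomes and BPD are analysed with no rule for infants who die; on observed days, an early death counts as a short stay

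*Combined protocol and SAP*

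**What the plan says.** The Outcomes section lists "days of hospitalization, days on noninvasive ventilation, days on supplemental oxygen, pre-discharge mortality" side by side, so mortality is an outcome in its own right and is not part of any of the others. The Abstract has a similar list, "days of hospitalization, days on noninvasive respiratory support, days on IMV, days on supplemental oxygen, mortality, need for surfactant", which adds days on invasive mechanical ventilation (IMV); the Outcomes section does not include that item.

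BPD also stands alone, as "incidence of stage III ROP and BPD". Its definition is given: "BPD will be defined according to the National Institutes of Health consensus definition as mild, moderate and severe BPD". Under Data collection it is assessed as "The incidence of BPD and ROP at a post-menstrual age of 36 weeks or at discharge".

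The analysis in Statistical methods is "Student's t-test for continuous data and compared proportions using Chi-squared test", with Fisher's exact test also named for categorical data. The only rule for missing values is multiple imputation of primary and secondary outcomes for infants lost to follow-up. Neither that section nor the study definitions in Appendix A3 mention death in connection with days or BPD. The plan has no composite of death with BPD, no alive-and-free measure, no survivors-only rule and no competing-risk method.

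**The concern.** Infants are enrolled from 26 weeks' gestation and mortality is a listed outcome, so the plan expects deaths. Death cuts short every day count. An infant who dies on day 3 has 3 hospital days and at most 3 oxygen days, and in a t-test on observed days those are among the best values in the trial. If one arm has more early deaths, that arm appears to have shorter stays and less support. If one arm prevents early deaths, it appears to have longer ones.

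For BPD, an infant who dies before 36 weeks and before discharge reaches neither assessment point. The plan does not say whether that infant counts as free of BPD, is left out, or is imputed. The Discussion hopes the trial will inform guidelines and reduce morbidity linked to IMV. BPD and support days are among the results that would be cited for that.

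**Working it through.** The documents give no death rate, time of death, length of stay or BPD rate, so there is no stated figure to reproduce. All rates and durations below are assumed. The 150 infants per arm come from Sample size calculation, and the 0.05 level from Statistical methods (taken as two-sided).

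**Day counts, formula.** Let survivors have mean S and standard deviation SD in both arms, let deaths occur at mean day d (standard deviation 2), and let m be the proportion dying.

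- Arm mean: (1 − m)·S + m·d
- Arm variance: (1 − m)(SD² + S²) + m(2² + d²) − mean²
- False difference between arms: (m_B − m_A)(S − d)

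The difference is zero when m_A = m_B with the same timing of death. It changes sign if deaths come later than the survivors' mean.

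**Hospital days, S = 45, SD = 20, d = 5, deaths 5% versus 10%.**

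- Means: 0.95 × 45 + 0.05 × 5 = 43.0 and 0.90 × 45 + 0.10 × 5 = 41.0, a difference of 2.0 days
- Variances: 456.2 and 504.4
- Standard error: √((456.2 + 504.4)/150) = 2.53, so difference/SE = 0.79
- Rejection: Φ(−1.96 + 0.79) + Φ(−1.96 − 0.79) = 12.4%

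| Deaths, arm A vs B | Hospital days: B falsely shorter by | Rejection | Oxygen days (S = 20, SD = 15, d = 3): B falsely fewer by | Rejection |
|---|---|---|---|---|
| 2% vs 5% | 1.2 | 7.9% | 0.5 | 6.0% |
| 5% vs 10% | 2.0 | 12.4% | 0.85 | 7.8% |
| 5% vs 15% | 4.0 | 34.1% | 1.7 | 16.4% |
| 5% vs 5% | 0 | 5.0% | 0 | 5.0% |

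**Simulation with skewed stays.** This used 4,000 trials per scenario, log-normal stay in survivors (median 40 days, log-SD 0.45) and deaths at a mean of 5 days. Mortality of 10% versus 5% gave a stay 1.9 days shorter and about 11% rejections. Mortality of 15% versus 5% gave 3.9 days and about 31%. Equal mortality gave 0.0 days and 4.9%. The two methods agree closely.

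**BPD.** Let b be the BPD rate among survivors, the same in both arms. Take b = 20% and deaths 5% (A) versus 10% (B).

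- Deaths scored as no BPD, b(1 − m): 19.0% vs 18.0%. Arm B looks 1.0 point better.
- BPD or death, b(1 − m) + m: 24.0% vs 28.0%. Arm B is 4.0 points worse.
- Survivors only: 20% vs 20%, equal by construction here.

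In general the first rule favours the arm with more deaths by b·(m_B − m_A), and the composite counts against it by (1 − b)·(m_B − m_A). For b from 15% to 40% and deaths from 2% vs 5% up to 5% vs 15%, the first ranges from 0.45 to 4.0 points and the second from 1.8 to 8.5 points.

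**Window for the remedy.** Counting free days up to 36 weeks' post-menstrual age would give an infant born at 26+0 a window of 10 weeks = 70 days, and one born at 33+6 a window of 2 weeks and 1 day = 15 days. A 33+6 infant needing no support could score at most 15, while a 26+0 infant supported for 30 days could score 40. The window therefore has to be the same length for everyone.

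**The case against.** The strongest reply is that the plan is silent rather than wrong. A reader might infer that it scores infants who die as having no BPD. No section says so. Since BPD is assessed at 36 weeks or discharge, such infants could equally be treated as not evaluable or as missing, and the day counts could be restricted to survivors. That objection stands, and for BPD the point is the absence of a rule. The gap still matters, because each default has a cost. Scoring no BPD rewards deaths. Restricting to survivors gives up the randomized comparison when mortality differs. Treating death as loss to follow-up would impute BPD and Bayley values for infants who died.

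Second, the bias needs unequal early mortality, and every input is assumed. This also stands; late deaths can push the other way. But the analysis has to be fixed before mortality is known.

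Third, mortality is reported separately, so a large imbalance would be seen. At 15% versus 5% and 150 per arm, a two-proportion test has about 83% power. At 10% versus 5% it has only about 38%, so a distorting imbalance can easily go unflagged. Seeing the imbalance also does not correct the p-values for days or BPD.

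Fourth, a reader might add that the t-test fails through skewness, taking one minus the pilot IMV rates (24.3% and 56.4%) to argue that roughly 44% to 76% of infants will have zero IMV days. The documents do not support this. The trial's need-for-IMV outcome covers 7 days, whereas IMV days are not so limited and later intubations would lower the figure. In the simulation with skewed stays, the t-test kept its 5% level when mortality was equal.

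**Conclusion.** The point holds as follows. The plan compares raw days and BPD by tests that take no account of death, and on observed days the t-test favours the arm with more early deaths. On the assumed inputs the false difference in stay is about 1 to 4 days, with 8% to 34% rejections, for mortality gaps of 3 to 10 percentage points; it is nil when mortality and its timing are equal. For BPD the plan does not settle how deaths count, and with equal BPD rates in survivors that choice decides which arm looks better.

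The size rests wholly on assumed death rates, times of death and stays; the direction for day counts rests on deaths being early. The finding concerns secondary outcomes and says nothing about the primary outcome. It is worth correcting before the data are analysed, because otherwise the rule could be chosen after results are seen.

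**What to change.** Add to Statistical methods:

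- **BPD.** Analyse BPD or death before 36 weeks' post-menstrual age as the comparison, and report BPD and death separately beside it.
- **Day counts.** Compare days alive and free of IMV (if it is kept as an outcome), of noninvasive support, of oxygen and of hospital. Use one window of the same length for every infant, counted from randomization and set in advance. Rank death worst. Use a rank test stratified by the four gestational-age randomization strata (for example van Elteren). State how infants discharged before the window ends are counted.
- **Raw days.** Report in survivors, as descriptive only.
- **Missing data.** State that multiple imputation does not apply to infants who died, including for Bayley scores.

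Also reconcile the Abstract and Outcomes lists on IMV days. Confirm that date of death and IMV days are recorded: the Data collection list names mortality but not its date, and omits IMV days. It refers to the appendix for more detail, but the appendix text available lists neither.

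The cost is wording, plus two data fields if they are not already captured. The downside is that composite and alive-and-free measures mix death with morbidity, so a difference may come from either; the components must therefore always be shown.
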